11.2 Clinical Laboratory Variables

Biochemistry, hematology, and urinalysis will be measured at the visits specified in [Table 1](#); the time points during each visit are specified in [Table 2](#), [Table 3](#), [Table 4](#), and [Table 5](#) for Cohorts A, B, C, and D, respectively. Baseline for clinical laboratory for SDTP is defined as the last non-missing scheduled assessment made prior to dosing in SDTP and baseline for MDTP is defined as the last non-missing scheduled assessment made prior to dosing in MDTP. Descriptive statistics for clinical laboratory values (in SI units) and changes from baseline at each assessment time point for quantitative variables will be presented by treatment group for the following clinical laboratory variables.

Hematology	Hematocrit, hemoglobin, red blood cells (RBC), platelet count, white blood cell count (WBC) – total and differential: total neutrophils (absolute), lymphocytes (absolute), monocytes (absolute), eosinophils (absolute), basophils (absolute)
Biochemistry	Sodium, potassium, glucose, creatinine, blood urea nitrogen (BUN), calcium, chloride, phosphorus, total CO ₂ (bicarbonate), albumin, total protein, ALT, AST, gamma- glutamyltransferase (GGT), ALP, total bilirubin, uric acid, β-hCG (females only).
Urinalysis	pH, specific gravity, blood, WBC, glucose, protein, ketones, bilirubin, nitrite, and leukocyte esterase.

Clinical laboratory test values are potentially clinically important (PCI) if they meet either the low or high PCI criteria listed in Table 6. The number and percentage of subjects with postbaseline PCI values will be tabulated by treatment group. The percentages will be calculated relative to the number of subjects with available baseline values and at least 1 postbaseline assessment. The numerator is the total number of subjects with at least 1 postbaseline PCI value. A supportive listing of subjects with postbaseline PCI values will be provided including the subject number, site, baseline, and postbaseline values.

Table 6 Criteria Potentially Clinically Important Laboratory Tests

Parameter	Lower Limit	Higher Limit
Hematology		
Hemoglobin	< 0.6 × LLN OR Decrease of ≥ 6% from baseline value	> 1.3 × ULN
Hematocrit	< 0.6 × LLN	> 1.3 × ULN
Leukocytes (WBC)	< 0.5 × LLN	> 2 × ULN
Neutrophils	< 0.5 × LLN OR < 40%	NA OR > 70%
Eosinophils	NA	> 4 × ULN OR >10%
Plateletes	< 0.4 × ULN	> 2 × ULN
Blood Chemistry		
Albumin	< 0.6 × LLN	NA
Total Protein	< 50g/ L	> 90 g/ L
ALT/ SGPT	NA	> 3 × ULN
AST/SGOT	NA	> 3 × ULN
ALP	NA	> 3 × ULN
Total bilirubin	NA	> 1.5 × ULN
Sodium	< 0.9 × LLN	> 1.1 × ULN
Potassium	< 0.85 × LLN	> 1.2 × ULN
Creatinine	NA	> 1.5 × ULN
BUN	NA	> 3 × ULN
Bicarbonate	< 0.5 × LLN	> 1.3 × ULN
Glucose	0.6 × LLN	> 3.5 × ULN
Calcium	< 0.7 × LLN	> 1.3 × ULN
Phosphorus	< 0.3229 mmol/L	> 1.6145 mmol/L
Chloride	< 0.8 × LLN	> 1.2 × ULN
URINALYSIS		
pH	< 4.5	> 7.2

Specific Gravity	< 0.9 × LLN	> 1.1 × ULN
Blood		> 5
WBC		> 5
Glucose		≥ 100 mg/dL
Protein		> 20 mg/dL
Bilirubine		Other than negative
Nitrite		Other than negative
Ketones		Other than negative
Leukocyte esterase		Small, moderate and large (eg other than negative OR trace)

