7.2.2.6 Clinical Laboratory Evaluations

All clinical laboratory assays will be performed according to the laboratory's normal procedures. Reference ranges are to be supplied by the laboratory and will be used to assess the clinical laboratory data for clinical significance and out-of-range pathological changes. The investigator should assess out-of-range clinical laboratory values for clinical significance, indicating if the value(s) is/are not clinically significant or clinically significant. Abnormal clinical laboratory values, which are unexpected or not explained by the subject's clinical condition, may, at the discretion of the investigator or sponsor, be repeated as soon as possible until confirmed, explained, or resolved. Any laboratory results that are determined to be clinically significant or indicative of an AE, as determined by the investigator, will be captured in the clinical database.

The following clinical laboratory assessments will be performed:

Biochemistry

Blood samples (8.5 mL) for serum biochemistry will be collected into a gel separator tube at the visits specified in [Table 1](#). The following parameters will be assessed:

Sodium	Total CO ₂ (Bicarbonate)
Potassium	Albumin
Glucose	Aspartate aminotransferase
Blood urea nitrogen	Alanine aminotransferase
Creatinine	Gamma-glutamyltransferase
Calcium	Alkaline phosphatase
Chloride	Total bilirubin

Phosphorus Uric acid

Total protein β -hCG^a

^a Females only. Only females of child-bearing potential ie, not postmenopausal or surgically sterile, as defined in Section 4.4.1, will be required to have β -hCG evaluated. Reported values of β -hCG that are >1.0 and <6.0 mIU/mL are less than the upper range for non-pregnant, post-menopausal female (7.0-8.3 mIU/mL) and are considered negative.

Hematology

Blood samples (4 mL) for hematology will be collected into an ethylenediaminetetraacetic acid tube at the visits specified in Table 1. The following parameters will be assessed:

Hemoglobin	Total neutrophils (absolute)
Hematocrit	Eosinophils (absolute)
Red blood cells	Monocytes (absolute)
Platelet count	Basophils (absolute)
White blood cell count (total and differential)	Lymphocytes (absolute)

Urinalysis

A urine sample for urinalysis will be collected at the visits specified in Table 1. The following parameters will be assessed:

pH	Blood	Nitrites
Glucose	Ketones	Leukocyte esterase
Protein	Bilirubin	Specific gravity

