Microscopic examination will be conducted if protein and/or blood is/are detected during urinalysis. At a minimum, the microscopic examination will consist of red blood cells, white blood cells, casts, and bacteria.

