2.3 Determination of Sample Size

A sufficient number of subjects will be screened to ensure the enrollment and completion of 84 subjects.

The number of subjects in this study is not based on statistical power considerations because the statistical analyses are primarily descriptive in nature. However, if at least 7 subjects complete each cohort, then there will be at least 65% to 85% probability of observing at least 1 occurrence of any AE with a true incidence rate for a given dose group of at least 15% to 25%, respectively.

It is estimated that dose escalation will occur for up to 3 dose levels (4 cohorts within each dose level). Each cohort will include 5 subjects randomized to active drug (SHP639) and 2 subjects randomized to placebo for an estimated total of at least 84 subjects.

For each cohort, the number of subjects will be increased as needed based on safety and IOP response to investigational product. Any cohort can be repeated to confirm findings with regard to safety or IOP response to investigational product.

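### The urine WBC row of the PCI tables can show an undefined percentage or one above 100%, because its denominator needs a baseline value that comes only from triggered microscopy and its numerator does not

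*SAP*

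**What the plan says.** **Collection (Protocol 7.2.2.6, Urinalysis).** The routine panel is introduced by "A urine sample for urinalysis will be collected at the visits specified in Table 1. The following parameters will be assessed". It has nine items: pH, glucose, protein, blood, ketones, bilirubin, nitrites, leukocyte esterase and specific gravity. White blood cells are not among them. They appear in the next step: "Microscopic examination will be conducted if protein and/or blood is/are detected during urinalysis", and "At a minimum, the microscopic examination will consist of red blood cells, white blood cells, casts, and bacteria".

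**Analysis (SAP 11.2 and Table 6).** The urinalysis variables are "pH, specific gravity, blood, WBC, glucose, protein, ketones, bilirubin, nitrite, and leukocyte esterase". Table 6 gives urine WBC its own upper PCI limit, > 5. This is a limit on the observed value, so it can be met without a baseline.

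**Percentage rule (SAP 11.2).** Denominator: "The percentages will be calculated relative to the number of subjects with available baseline values and at least 1 postbaseline assessment". Numerator: "The numerator is the total number of subjects with at least 1 postbaseline PCI value". On baseline, "baseline for MDTP is defined as the last non-missing scheduled assessment made prior to dosing in MDTP", with the same wording for the single-dose period (SDTP). No rule covers tests done only on a trigger, a PCI value without a baseline, or an empty denominator.

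**Outputs (SAP 16).** Table 14.3.4.2.5 is the urinalysis PCI table for the SDTP. Table 14.3.4.2.6 is the one for the multiple-dose period (MDTP) and is also marked as an interim output.

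**The concern.** A percentage needs its numerator to be a subset of its denominator. For items measured in everyone at every urinalysis visit, the loose numerator wording does little harm, because almost every subject has a baseline. Urine WBC differs: a subject whose predose urine shows no protein or blood has no baseline WBC at all. Inclusion criterion 7 makes this more likely, since entry requires no clinically significant or relevant abnormality on evaluations that include urinalysis.

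The mismatch therefore falls on subjects whose abnormality is new on treatment, the cases a PCI table is meant to show. Safety and tolerability are the primary objective, and groups are small (5 active and 2 placebo subjects per cohort), so one or two such subjects are enough to make the printed percentage meaningless.

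**Working it through.** The plan states no figure for this row, so there is nothing to reproduce. Steps 1 and 2 need no assumption about rates; step 3 does.

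**1. Classify the subjects in a group.**
- a: baseline WBC present, postbaseline WBC > 5
- b: baseline WBC present, postbaseline WBC measured, none > 5
- d: no baseline WBC, postbaseline WBC > 5
- e: everyone else

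Under SAP 11.2 the denominator is a + b, the numerator is a + d, and the percentage is 100(a + d)/(a + b). It exceeds 100% when d > b with a + b > 0. It is undefined when a + b = 0.

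**2. Worked cases, 5 active subjects.**
- No predose microscopy in anyone, one subject with a postbaseline WBC > 5: a = b = 0, d = 1, giving 1/0.
- One subject with baseline and postbaseline microscopy and no PCI value, two with no baseline and a PCI value: b = 1, d = 2, giving 2/1 = 200%.

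**3. How often? Illustration only.** Let p be the chance that a sample triggers microscopy and q the chance that a triggered sample shows WBC > 5. The documents give neither. The MDTP schedule for Cohorts B to D has 3 predose samples (Screening, Day -2, Day 1 predose) and 6 postbaseline samples (Days 7, 14, 21, 26, 27, 29). With independent visits, q = 30% and n = 5:

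| Quantity | Formula | p = 5% | p = 10% | p = 20% |
|---|---|---|---|---|
| Baseline WBC exists | B = 1 − (1 − p)^3 | 0.143 | 0.271 | 0.488 |
| Any postbaseline WBC | M = 1 − (1 − p)^6 | 0.265 | 0.469 | 0.738 |
| Expected denominator | 5BM | 0.19 | 0.64 | 1.80 |
| Expected numerator | 5[1 − (1 − pq)^6] | 0.43 | 0.84 | 1.55 |
| Empty denominator | (1 − BM)^5 | 0.83 | 0.51 | 0.11 |
| PCI subject has no baseline | (1 − p)^3 | 0.86 | 0.73 | 0.51 |

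Exact enumeration over p = 5–30% and q = 20–50% (same layout, n = 5) gives these ranges:
- percentage undefined with at least one PCI subject: 0.01 to 0.40
- percentage above 100%: 0.01 to 0.42
- at least one numerator subject outside the denominator: 0.23 to 0.75

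These figures are fragile in two ways.
- *Independence.* If p varies between subjects (a beta distribution with mean p), the last row of the table falls from 86/73/51% to about 43/39/31% at a within-subject correlation of 0.3, and to about 28/26/21% at 0.5.
- *Layout.* The SDTP has 2 predose samples (Screening, Day -2) and, counting only Day 2, 1 postbaseline sample. Then B = 1 − (1 − p)^2, M = p, and under independence the denominator is empty with probability (1 − BM)^5 = 0.98/0.91/0.69. Cohort A's MDTP has more predose samples than Cohorts B to D, and pooled placebo groups are not of size 5.

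**4. Effect of two repairs on the cases in step 2.**
- Restricting the numerator to a gives 0/0 and 0/1. The percentage can no longer exceed 100%, but every new case is lost.
- Using all subjects with a postbaseline urinalysis as the denominator (here all 5) gives 1/5 = 20% and 2/5 = 40%. Every PCI case is kept and the result always lies between 0 and 100%.

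**The case against.** The strongest reply is that the rule need not be read this way. A baseline value could mean any baseline urinalysis rather than a baseline for that parameter, which would put nearly every subject in the denominator. Many programmers would also draw the numerator from the denominator by habit. SAP 1 defers table specifications to a separate document, and both tables are marked as sponsor-standard outputs, so the matter may be settled there. Finally, SAP 11.2 lists WBC among variables measured at the Table 1 visits, which could suggest routine measurement.

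None of these readings is in the text. Table 6 works by parameter, the numerator is worded as a total number of subjects, and the protocol, which governs collection, makes microscopy conditional. The any-urinalysis reading would count untested subjects as not PCI without saying so, and the restricted-numerator habit would drop the new cases.

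What stands is the limit on impact. A reader might infer that new findings are hidden, or that active and placebo could not be compared on urine WBC. The documents do not support either. SAP 11.2 tabulates the number as well as the percentage, the unrestricted numerator counts each new case, and each PCI subject is listed with baseline and postbaseline values (Listing 16.2.8.1.3). The objection that any frequency rests on assumed trigger rates and independent visits also stands.

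**Conclusion.** The defect is real and minor. Followed literally, SAP 11.2 can give an undefined urine WBC percentage or one above 100% in Tables 14.3.4.2.5 and 14.3.4.2.6. This rests on two readings: that white cells come only from triggered microscopy, as Protocol 7.2.2.6 states, and that the baseline requirement applies parameter by parameter, as Table 6 implies.

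A reader might take the step 3 probabilities as the expected size of the problem. They are not: the documents give no trigger rate, no positivity rate and no within-subject correlation, and the 3-and-6 sample layout does not fit the SDTP table.

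One descriptive row is materially affected. Counts and listings are intact. Sample size and inference are untouched, since "The number of subjects in this study is not based on statistical power considerations because the statistical analyses are primarily descriptive in nature".

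**What to change.** In SAP 11.2, for urine WBC and any other item obtained only by microscopy:
- Take as denominator all subjects with at least one postbaseline urinalysis in the period, with no baseline requirement.
- Count samples in which microscopy was not triggered as not PCI.
- Footnote this rule in both tables, with the number of subjects who had microscopy.

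For the other laboratory items, state that the numerator is counted among subjects in the denominator. This will have little practical effect.

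The cost is a short addition to the SAP text, a footnote and a small programming change. No new data are needed. The downside is that untriggered samples are assumed not PCI, so raised white cells in urine without protein or blood would not count in this row. The footnoted microscopy count lets the reader see how much rests on that assumption.

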11.3 Vital Signs

Blood pressure, pulse rate and body temperature will be measured at the visits specified in Table 1; the time points during each visit are specified in Table 2, Table 3, Table 4, and Table 5 for Cohorts A, B, C, and D, respectively. Baseline for vital signs for SDTP is defined as the last non-missing scheduled assessment made prior to dosing in SDTP and baseline for MDTP is defined as the last non-missing scheduled assessment made prior to dosing in MDTP. Additional blood pressure and pulse rate measurements may be performed, as determined by the investigator, in order to ensure appropriate monitoring of subject safety and accurate recording of vital sign measurements. Any changes from baseline that are deemed clinically significant by the investigator are to be recorded as an AE.

Descriptive statistics for vital signs (systolic and diastolic blood pressure, pulse rate, and body weight) and their changes from baseline at each postbaseline visit and at the end of study will be presented by treatment group. Vital sign results will be listed by individual subject.

Vital sign values will be considered PCI if they meet both the observed value criteria and the change from baseline criteria listed in Table 7. The number and percentage of subjects with PCI postbaseline values will be tabulated by treatment group and overall by dosing regimen in the Safety set. Percentages will be calculated relative to the number of subjects with baseline and at least 1 postbaseline assessment. The numerator is the total number of subjects with at least 1 PCI postbaseline vital sign value. A supportive listing of subjects with postbaseline PCI values will be provided including the subject number, site, baseline, and postbaseline PCI values.

Table 7 Criteria for Potentially Clinically Important Vital Signs

Vital Sign Parameter	Flag	Criteria ^a	
		Observed Value	Change from Baseline
Systolic blood pressure (mmHg)	High	≥ 160	Increase of ≥ 20
	Low	≤ 90	Decrease of ≥ 20
Diastolic blood pressure (mmHg)	High	≥ 105	Increase of ≥ 15
	Low	≤ 50	Decrease of ≥ 15
Pulse rate (beats per minute)	High	≥ 100	Increase of ≥ 15
	Low	≤ 40	Decrease of ≥ 15
Weight (kg)	High	-	Increase of ≥ 7%
	Low	-	Decrease of ≥ 7%

^a A postbaseline value is considered as a PCI value if its meets both criteria for observed value and change from baseline.

11.4 Electrocardiogram (ECG)

Twelve-lead ECGs will be performed at the visits specified in [Table 1](#); the time points during each visit are specified in [Table 2](#), [Table 3](#), [Table 4](#), and [Table 5](#) for Cohorts A, B, C, and D, respectively. Descriptive statistics for ECG variables (heart rate, PR interval, RR interval, QRS interval, QT interval, and QTc interval) and their changes from baseline at each assessment time point will be presented by treatment group and overall by dosing regimen in the Safety set. Baseline for ECG for SDTP is defined as the last non-missing scheduled assessment made prior to dosing in SDTP and baseline for MDTP is defined as the last non-missing scheduled assessment made prior to dosing in MDTP. QTc interval will be calculated using both Bazett ($QTcB=QT/(RR)^{1/2}$) and Fridericia ($QTcF=QT/(RR)^{1/3}$) corrections. ECG interpretation will be summarized by visit and cohort. ECG results and interpretation will be listed by individual subject.

If the QTcF interval (calculated online on site) is increased by >45 msec from the baseline or an absolute QTcF value is >500 msec for any scheduled ECG, then 2 additional ECGs will be collected, approximately 2-4 minutes apart, to confirm the original measurement. If either of the QTcF values from these repeated ECGs remains above the threshold value (>45 msec from the baseline; or is >500 msec), then a single ECG must be repeated at least hourly until QTcF values from 2 successive ECGs fall below the threshold value that triggered the repeat measurement. When triplicate ECGs are collected, the mean of the triplicate measurements should be used to trigger the decision to collect follow-up ECGs.

If QTcF values remain above 500 msec (or >45 msec from the baseline) for >4 hours (or sooner at the discretion of the investigator) or QTcF intervals get progressively longer, the subject should undergo continuous ECG monitoring. A cardiologist should be consulted if QTcF intervals do not return to <500 msec (or to <45 msec above the baseline) after 8 hours of monitoring (or sooner at the discretion of the investigator).

If a machine-read QTcF/QTcB value is prolonged, as defined above, repeat measurements may not be necessary if a qualified physician's interpretation determines that the QTcF/QTcB values are in the acceptable range.

Electrocardiogram variable values will be considered PCI if they meet or exceed the upper limit values listed in Table 8. The number and percentage of subjects with postbaseline PCI values will be tabulated by treatment group and overall by dosing regimen in the Safety set. The percentages will be calculated relative to the number of subjects with available non-PCI baseline and at least 1 postbaseline assessment. The numerator is the total number of subjects with at least 1 PCI postbaseline ECG value. A listing of all subjects with postbaseline PCI value will be provided including the subject number, site, baseline, and postbaseline PCI values.

Table 8 Criteria for Potentially Clinically Important ECG Values

ECG Parameter (unit)	Flag	Criteria	
		Observed Value	Change from Baseline
Heart rate (bpm)	HIGH	≥ 100	Increase of ≥ 15
	LOW	≤ 40	Decrease of ≥ 15
QRS Interval (msec)	HIGH	> 200	
	LOW	< 120	
PR Interval (msec)	HIGH	> 220	Increase of > 20
	LOW	< 100	
QTc Interval (msec)	MEN HIGH	> 430	Increase of > 30
	WOMEN HIGH	> 450	Increase of > 30
	MEN LOW	< 330	
	WOMEN LOW	< 340	

11.5 Antidrug Antibody Testing

A blood sample of approximately 6 mL will be collected to test for antidrug antibodies (ADA) in serum at the visits specified in Table 1. On dosing days, samples will be collected before the first dose of the day. Any subject with newly developed antidrug antibodies at the Day 60 assessment may require follow-up. Results of ADA testing will be listed by individual subject. The summarization format will be based on the data result type.

11.6 Other Safety Variables

11.6.1 Drop comfort assessment

Drop comfort assessment should be performed immediately after instillation of investigational product and before IOP assessment (which requires topical anesthetic). Drop comfort assessment

will be measured at the visits specified in Table 1; the time points during each visit are specified in Table 2, Table 3, Table 4, and Table 5 for Cohorts A, B, C, and D, respectively.

The drop comfort assessment will be performed for each eye (study eye, non-study eye, and either eye) except for Cohort A during the SDTP, when only the study eye will be assessed. For either eye summaries, the assessment denoting the most discomfort (e.g., greater value) will be summarized. The assessment will be performed immediately and 1, 2, and 3 minutes after instillation of the investigational product. The subject will be asked to rate drop comfort on a scale of 0-10, where 0=very comfortable and 10=very uncomfortable.

If the score is not ≤ 3 at minute 3, the drop comfort assessment should be repeated at 5, 10, and 15 minutes after dosing until the score is ≤ 3 . If the score is >3 at 15 minutes after dosing, it should be recorded as an AE.

Descriptive statistics for drop comfort scores at each assessment time point during the SDTP will be presented for study eye by treatment group. Descriptive statistics for drop comfort scores at each assessment time point during the MDTP will be presented by eye (study eye, non-study eye, either eye) and by treatment group. The score of drop comfort at each assessment visit and time point will be listed by individual subject.

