If the score is not ≤ 3 at minute 3, the drop comfort assessment should be repeated at 5, 10, and 15 minutes after dosing until the score is ≤ 3 . If the score is >3 at 15 minutes after dosing, it should be recorded as an AE.

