9.4 Statistical Analysis Process

The study will be analyzed by the sponsor or its agent.

The statistical analysis plan (SAP) will provide the statistical methods and definitions for the analysis of the PK, PD, and safety data, as well as describe the approaches to be taken for summarizing other study information such as subject disposition, demographics and baseline characteristics, investigational product exposure, and prior and concomitant medications. The SAP will also include a description of how missing, unused and spurious data will be addressed.

To preserve the integrity of the statistical analysis and study conclusions, the SAP will be finalized before database lock.

All statistical analyses will be performed using SAS[®] software (SAS Institute, Inc, Cary, NC 27513).

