15. DATA HANDLING CONVENTIONS

15.1 General Data Reporting Conventions

Continuous variables will be summarized using the following descriptive statistics: n, mean, median, standard deviation, minimum, maximum. Categorical and count variables will be summarized by the number of subjects (n) and the percent of subjects in each category. Percentages will be presented as whole numbers.

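### Drop comfort means after minute 3 would cover only eyes still uncomfortable at their previous score, because SAP 11.6.1 has no rule for eyes that have recovered

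*SAP*

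**What the plan says.** SAP 11.6.1 defines the scale: "rate drop comfort on a scale of 0-10, where 0=very comfortable and 10=very uncomfortable". Four time points apply to everyone: "The assessment will be performed immediately and 1, 2, and 3 minutes after instillation of the investigational product". The later ones are conditional. An eye above 3 at the last of these four is followed further: "the drop comfort assessment should be repeated at 5, 10, and 15 minutes after dosing until the score is ≤ 3". Protocol 7.2.2.3 and the footnotes to the schedule tables carry the same rule. A score still above 3 at 15 minutes is recorded as an AE.

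For the analysis, SAP 11.6.1 states for the multiple-dose period: "Descriptive statistics for drop comfort scores at each assessment time point during the MDTP will be presented by eye". That summary covers the non-study eye as well as the study eye, plus an either-eye version, within each treatment group. The single-dose period has its own sentence: "Descriptive statistics for drop comfort scores at each assessment time point during the SDTP will be presented for study eye by treatment group". SAP 15.1 says what these statistics are: "Continuous variables will be summarized using the following descriptive statistics: n, mean, median, standard deviation, minimum, maximum". All scores are also listed by subject.

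Protocol 9.4 promises: "The SAP will also include a description of how missing, unused and spurious data will be addressed". SAP section 15 gives rules for partial dates, AE severity, AE causality and coded laboratory values, but none for comfort scores. SAP 11.6.1 gives no denominator, no handling of eyes no longer scored, and no restriction to the first four time points.

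**The concern.** From 5 minutes on, the outcome decides who is measured. An eye leaves the measurement because it has become comfortable, so its absence carries information. A mean over the scores that remain is discomfort among those not recovered at the preceding assessment. It is not discomfort in the treatment group, yet it would stand in the same table, under the same label, as the all-subject means at minutes 0 to 3.

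Tolerability is part of the primary objective (Protocol 2.2.1). Protocol 1.3 names local ocular discomfort as the anticipated toxicity. The MDTP drop comfort table (14.3.7.1.2) is marked for interim output in SAP section 16, and Protocol 9.5 says the Part 1 interim is meant to help identify safe and tolerable doses. The late rows could show discomfort rising after instillation when it is resolving, or rank two doses in the wrong order.

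**Working it through.** The documents give no figure for drop comfort to reproduce. The check applies their scoring rule to constructed scores. **All scores below are assumptions, not trial data.**

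**Inputs.** Scoring rule and scale: SAP 11.6.1. Statistics: SAP 15.1. Group size: 5 active subjects per cohort (SAP 2.3). One eye per subject.

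**Formulas.** Let y(i,t) be the score of subject i at minute t.
- Scored at 5: those with y(i,3) > 3. Scored at 10: those scored at 5 with y(i,5) > 3. Scored at 15: those scored at 10 with y(i,10) > 3.
- Tabulated mean at t = sum of y(i,t) over those scored ÷ number scored.
- All-subject mean at t = sum of y(i,t) over all 5 ÷ 5.

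**Example A: all five improve by one point from minute 3 to minute 5.**

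| Minute | True scores | All-subject mean | Tabulated mean (n) | Above 3, of all 5 |
|---|---|---|---|---|
| 3 | 1, 1, 2, 2, 7 | 13/5 = 2.6 | 2.6 (5) | 1/5 = 20% |
| 5 | 0, 0, 1, 1, 6 | 8/5 = 1.6 | 6.0 (1) | 20% |
| 10 | 0, 0, 0, 0, 5 | 5/5 = 1.0 | 5.0 (1) | 20% |
| 15 | 0, 0, 0, 0, 4 | 4/5 = 0.8 | 4.0 (1) | 20% |

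From minute 3 to minute 5 the tabulated mean rises by 6.0 − 2.6 = 3.4 while the true mean falls by 2.6 − 1.6 = 1.0.

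**Example B: two subjects above 3 at minute 3.** Minute-3 scores are 1, 2, 3, 5, 7, with mean 18/5 = 3.6. The two rescored subjects score 4 and 6 at 5 minutes, then 3 and 5 at 10. The last one scores 4 at 15.
- Tabulated: 3.6 (n=5), (4+6)/2 = 5.0 (n=2), (3+5)/2 = 4.0 (n=2), 4.0 (n=1).
- Above 3, counting those already at 3 or less as recovered: 2/5 = 40%, 40%, 20%, 20%.

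**Between groups.** At minute 5, group B has twice the proportion above 3 (40% against 20%), yet its tabulated mean is lower (5.0 against 6.0). The order at minute 3 was the reverse (B 3.6, A 2.6).

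**Empty rows.** With minute-3 scores 1, 1, 2, 2, 5 and the fifth subject scoring 4 and then 3, the rows read 2.2 (n=5), 4.0 (n=1), 3.0 (n=1) and nothing at 15 minutes.

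**How often.** This was simulated with 40,000 groups per setting. Uncomfortable subjects scored 4-10 at minute 3 and the others 1-3, uniformly. Each then improved by 1 to 3 points, with a floor of 0. The proportion above 3 at minute 3 was assumed to be 10%, 20% or 40%. Among groups with anyone scored at 5 minutes, the tabulated mean rose from minute 3 to minute 5 in 82%, 79% and 66% of groups of 5. In groups of 15 the figures were 92%, 95% and 87%.

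**Carry-forward.** In example A, holding recovered subjects at their last score gives 2.6, 2.4, 2.2, 2.0. This does not rise, but it misses the true 2.6, 1.6, 1.0, 0.8, because it fills in values nobody measured.

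**The case against.** Several points on the other side stand.

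- **The table shows n.** If no repeat is missed, n at 5 minutes is the number above 3 at minute 3, and n at 10 minutes is the number still above 3 at 5. A careful reader can rebuild most of the proportions, and the listing holds every score. This lets the problem be detected. It does not make the late means comparable, and it fails if repeats are missed.
- **The tail has its own route.** A score above 3 at 15 minutes becomes an AE, summarized as a percentage of subjects. A reader might infer that no comparison is possible after minute 3. The documents do not support that: persistent discomfort can be compared through the AE tables. Discomfort that resolves between 3 and 15 minutes is not captured that way.
- **A reader might infer upward bias in every group.** That goes too far. If all eyes are above 3 at minute 3, all are scored at 5 and there is no selection. If none are, there is no mean to bias. A sharp fall among the few rescored can also offset the selection.
- **A reader might infer that a dose decision could turn on these means.** Protocol 4.5.4 and 6.2.3.2 use AEs, corneal haze, IOP limits and completer counts. SAP Figure 1 says tolerability is considered at escalation meetings, but no comfort threshold appears anywhere.
- **The denominator is inferred.** SAP section 1 places table specifications in a separate document, which may settle it. Read literally, SAP 15.8 maps everything from just after 0 to 15 minutes to the 0-minute time point and keeps the assessment closest to plan, so no late row would exist. It would also remove the planned 1, 2 and 3 minute rows, so it cannot be what 11.6.1 intends.

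**Conclusion.** The point holds, with moderate impact. If the 5, 10 and 15 minute rows are tabulated on observed scores, their means describe an outcome-selected subset. They are typically higher than the all-subject mean and can rise from minute 3 to minute 5 while every subject improves. They should not be compared between doses or with placebo. The immediate and 1, 2 and 3 minute summaries are unaffected.

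This rests on two readings: that 11.6.1 governs over 15.8 for these time points, and that silence on recovered eyes means observed scores only. The size in the actual trial depends on how many eyes exceed 3 at minute 3, which the documents do not give. Because the analysis is descriptive and no rule uses these means, the risk is a misleading tolerability table rather than a wrong formal decision.

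**What to change.** In SAP 11.6.1:

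1. Restrict mean, SD and the other continuous summaries to the immediate and 1, 2 and 3 minute scores.
2. For 5, 10 and 15 minutes, report the number and percentage of all dosed subjects with a score above 3, counting those already at 3 or less as recovered. Do this separately for study eye, non-study eye and either eye in the MDTP, and for the study eye in the SDTP. Count subjects within each eye category; do not pool eyes.
3. Add the time to first score of 3 or less, with those still above 3 at 15 minutes shown as not reached.
4. Do not use carried-forward means as the main summary.
5. State whether one eye above 3 triggers repeats in both eyes, since the either-eye results after minute 3 depend on it.
6. Exempt drop comfort from the 0-minute window in SAP 15.8, or otherwise reconcile that window with the 11.6.1 time points.

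The cost is SAP wording and one revised table shell, with no new data. The remaining assumption is that a recovered eye stays at 3 or less through 15 minutes. The scoring rule already makes that assumption when it stops measuring, and the time to first score of 3 or less does not need it.
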